12.4.1 Analysis Population

Analysis will be carried out in all patients who complete protocol procedures. Patients who are lost to follow-up and who do not have a scan within +/-6 months of the 12-month time point will be excluded from analysis. Patients who develop inflammatory lung conditions unrelated to radiotherapy (i.e. pneumonia, ARDS, drug-induced pneumonitis, etc.) will be excluded from the final endpoint analysis if the area of unrelated inflammation impedes scoring of fibrosis severity of the irradiated lesion.

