- Severity of radiation induced pulmonary fibrosis is degree of fibrosis after SABR
- See Phase 1 definitions for the rest of the objectives

Analytic plan for primary objective:

Phase 1:

A safe dose of fresolimumab is reached when $\leq 10\%$ of the patients receiving fresolimumab plus SABR develops DLTs, defined as CTCAE v4 grade 3 or higher radiation pneumonitis and bronchopulmonary hemorrhage.

Phase 2:

Rate of radiation-induced pulmonary fibrosis is defined as percentage of patients with a moderate-to-severe level of fibrosis. Presence of fibrosis will be determined by CT imaging after treatment.

Analytic plan for secondary objectives:**Phase 1:**

- Potential adverse events will be monitored by treating physicians at each follow-up visit, and scored using CTCAE v4 with type and grade
- Post-treatment changes in pulmonary function will be evaluated by changes in pulmonary function test (PFT) at enrollment, 6-month, and 12-month follow-up
- Recurrence rates will be evaluated by follow-up CT imaging studies up to 1 year
- Progression-free survival will be evaluated by following the above imaging results at each follow-up visit up to 1 year
- Pharmacokinetics (PK) of fresolimumab will be determined by measurement of drug level in blood samples. Blood sample will be collected once before fresolimumab administration and again within 1-4 hours post administration.
- Rate of radiation induced pulmonary fibrosis is defined as percentage of patients with a moderate-to-severe level of fibrosis. Presence of fibrosis will be determined by CT imaging after treatment.
- Pattern of radiation-induced pulmonary fibrosis will be scored using the "Late Radiation Fibrosis Score" developed by Dahele, *et al.* [2]

Phase 2:

Please see Phase 1 definitions for the objectives

Sample size justification:**Phase 1:**

Post-SABR pneumonitis is expected to occur in $\leq 10\%$ of patients with stage I disease. Based on this percentage, we propose to start out with a cohort of 5 patients at the pre-selected dose of 3mg/kg of fresolimumab. If one patient develops DLT, then 5 more patients will be enrolled at the same dose to make a total of 10 patients. If no more patients experience DLT, then the total percentage of patients experiencing DLT is 10% and is considered acceptable for toxicity.

Phase 2:

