12.4.2. Analysis Plan

Approximately 60% of SABR patients develop acute radiologic changes in the lung at 3 months [16]. Late radiologic changes, reflecting fibrosis, are more frequent in SABR patients at 1 year [15]. Our institutional experience revealed the presence of moderate-to-severe late radiation induced fibrosis in ~75% of patients treated with SABR (50 Gy in 4 fractions) via VMAT technique at 1 year.

Primary analysis: The outcome of moderate-to-severe radiologic fibrosis rate will be tested in evaluable patients in a one-sample one-sided test of proportion comparing the observed rate, which is expected to be at most 58%, to the historically observed rate of ~75%. The observed rate and the 95% confidence interval calculated using the exact method will be reported.

Secondary analysis: Local control at 12 months will be estimated along with a one-sided lower 95% confidence bound to allow an informal assessment of the null hypothesis that the proportion is larger than 80%. Patients with distant progression before local failure will be censored one day after the last imaging study; patients who die before local control will be censored at the time of death. These definitions are used for comparability. Cumulative incidence estimates for local failure and other failure type will also be presented.

Time to event data (local control, PFS, time to progression) will be evaluated using Kaplan-Meier estimates with 95% confidence intervals at multiples of 12 months based on Greenwood's formula with a log transform. Confidence intervals for median times to event, if relevant, will be constructed using the method of Brookmeyer and Crowley.

Proportions (eg, proportion of patients with grade 4 or higher toxicity) will be estimated along with 95% exact confidence intervals. Patient clinical and demographic characteristics will be reported with the appropriate summary statistic (mean, range, proportion, etc.) Adverse events will be tabulated by organ system and severity.

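### Section 12.4.1 applies a completer rule and a lost-to-follow-up exclusion to all analysis without naming an endpoint, leaving the final Phase 2 adverse event, PFS and local control sets open

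*Combined protocol and SAP*

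**What the plan says.** Section 12.4.1 is the only analysis-population section. It contains three sentences.

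- The first is a general rule: "Analysis will be carried out in all patients who complete protocol procedures". The procedures are not defined, and neither a phase nor an endpoint is named.
- The second says that patients lost to follow-up who "do not have a scan within +/-6 months of the 12-month time point will be excluded from analysis". No endpoint is named here either.
- The third concerns lung inflammation judged unrelated to radiotherapy. Patients with pneumonia, ARDS, "drug-induced pneumonitis, etc.) will be excluded from the final endpoint analysis if the area of unrelated inflammation impedes scoring of fibrosis severity". This one is tied to fibrosis scoring.

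Section 10.1 repeats the second and third sentences in the fibrosis-scoring text, without the first.

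Section 12.4.2 says that the primary fibrosis rate "will be tested in evaluable patients in a one-sample one-sided test of proportion". For local control it says "Patients with distant progression before local failure will be censored one day after the last imaging study" and "patients who die before local control will be censored at the time of death", and adds "Cumulative incidence estimates for local failure and other failure type will also be presented". Local control, PFS and time to progression are to be estimated by Kaplan-Meier. Toxicity proportions get exact confidence intervals, and the only denominator given is patients.

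Section 4.2.5 continues follow-up where feasible after study treatment stops. Section 6 foresees skipped fresolimumab doses. The study calendar in Section 9 runs to a CT and PFT at month 12.

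**The concern.** A completer rule suits an endpoint that needs a month-12 scan. It does not suit adverse events or time-to-event outcomes, because patients who die, progress or stop for toxicity are often those who do not complete. As written, the rule covers all analysis and leaves the analyst to decide who counts.

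The trial is open-label and single-arm, so no control group is affected by the same rule. The final Phase 2 toxicity rates, PFS and local control could then describe a selected group. The lost-to-follow-up sentence adds a second difficulty: Kaplan-Meier would ordinarily use such a patient's time up to last contact, whereas the sentence removes the patient altogether.

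**Working it through.** **Step 1. Set the rules side by side.** Each row is a type of patient the protocol itself foresees.

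| Patient | 12.4.1, procedures include follow-up | 12.4.1, procedures mean treatment only | What other sections need |
|---|---|---|---|
| Fully treated, dies at month 5 | Dropped | Kept | 12.4.2 censors at death for local control |
| Fully treated, distant progression, later visits missed | Dropped | Kept | 12.4.2 censors for local control; a PFS event under 10.2 |
| Stops study treatment for toxicity, still followed | Dropped | Dropped | Follow-up continues under 4.2.5; toxicity belongs in the 12.4.2 tables |
| Lost at month 4, no scan in the window | Dropped | Dropped by the second sentence | Kaplan-Meier would ordinarily censor at last contact |
| Scan at month 9, no month-12 visit (calendar window +/- 2 weeks) | May be dropped | Kept | Scan lies within 12 +/- 6 months, so the scan rule does not exclude it |

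Neither reading of the first sentence gives a suitable set for safety and time-to-event results. The explicit censoring rules in 12.4.2 are written for local control. Section 10.2 defines PFS without a censoring rule, and no section names a set for the final Phase 2 adverse event tables.

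**Step 2. Which results have their own denominators.** The Phase 1 DLT criterion in the Synopsis is a share "of the patients receiving fresolimumab plus SABR develops DLTs", with cohort counts in 4.2.1. Section 7.12 sets its own denominators for the 25-patient pneumonitis and hemorrhage check and for the first-10 reviews of recurrence and new malignancy. None of these depends on 12.4.1.

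**Step 3. Safety illustration. All counts are invented.** Take 50 treated patients, 6 with an event and 5 non-completers. All treated: 6/50 = 12.0%. Completers only:

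- no non-completer had the event: 6/45 = 13.3%
- two did: 4/45 = 8.9%
- all five did: 1/45 = 2.2%

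The rate can move either way.

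**Step 4. Primary test.** Inputs: N = 50, 75% against 60%, one-sided 10%, 80% power (12.5.2); expected rate at most 58% (12.4.2).

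The plan's own figure first. Without continuity correction, n = [(1.2816 x sqrt(0.75 x 0.25) + 0.8416 x sqrt(0.60 x 0.40)) / 0.15]^2 = 41.6. With correction, n' = (n/4) x [1 + sqrt(1 + 2/(0.15n))]^2 = 48.0, so 49, and power at 50 is 81.3%. The stated N = 50 is therefore reproduced within rounding and is not in question.

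Now an exact binomial test, which is an assumption because 12.4.2 says exact only for the confidence interval. Let k be the number excluded, n = 50 - k, and c the largest count with P(X <= c | n, 0.75) <= 0.10. In the worst case every excluded patient has moderate-to-severe fibrosis and the true rate is 75%. The false-positive rate is then P(X <= c + k | 50, 0.75).

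| k | n | c | Size, neutral exclusions | Power at 60% | Power at 58% | Worst-case false positive |
|---|---|---|---|---|---|---|
| 0 | 50 | 33 | 9.8% | 84.4% | 90.3% | – |
| 1 | 49 | 32 | 8.4% | 81.6% | 88.2% | 9.8% |
| 2 | 48 | 31 | 7.0% | 78.6% | 85.8% | 9.8% |
| 3 | 47 | 30 | 5.9% | 75.1% | 83.1% | 9.8% |
| 4 | 46 | 30 | 9.0% | 80.8% | 87.4% | 16.3% |
| 5 | 45 | 29 | 7.5% | 77.5% | 84.8% | 16.3% |
| 6 | 44 | 28 | 6.3% | 73.9% | 81.8% | 16.3% |
| 7 | 43 | 28 | 9.6% | 79.9% | 86.5% | 25.2% |

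Exclusions unrelated to severity do not raise the false-positive rate. Inflation above 10% needs at least 4 exclusions, all moderate-to-severe. Starting from 50 may also be pessimistic. Enrollment is 55 to 60 (12.5.1), Phase 1 included (2.4). If Phase 1 patients count towards the 50, which is not stated, 5/55 = 9.1% to 10/60 = 16.7% could be lost and 50 would remain.

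**The case against.** The strongest reply is that the first sentence means completion of treatment. Section 4.3 uses the word procedures for SABR delivery and planning, and 7.12 mentions follow-up separately when it means follow-up. On that reading, deaths and progressions after treatment stay in and most of the conflict with the 12.4.2 censoring rules goes. This stands to the extent that a reader who infers a flat contradiction between 12.4.1 and 12.4.2 goes too far: the conflict depends on a term the documents do not settle. A reader may also fairly let the specific local control rules in 12.4.2 prevail. But the treatment-only reading still drops those who stop early for toxicity, and it leaves the lost-to-follow-up sentence untouched.

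Second, the primary set is mostly fixed by the two exclusions in 10.1 and 12.4.1. The explicit +/-6-month window shows that scans away from month 12 are meant to count. This also stands. What remains is that the general completer sentence should not be able to override the window.

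Third, a reader might infer that a possible study-drug pneumonitis would go unrecorded once it makes a lesion unscorable. It would not. Adverse events are collected to 30 days after last treatment (7.3), toxicity is evaluated to month 12 (Section 9), and related serious events are reportable outside the 30-day period too (7.5). What is missing is a required count of exclusions by cause.

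**Conclusion.** The point holds as a defect in a stated rule, and it should be fixed. Followed as written, 12.4.1 can remove early stoppers, losses to follow-up and, on one reading, early deaths and progressions from results that need them. The results affected are the final Phase 2 adverse event tables, PFS and the other time-to-event estimates.

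Three stronger inferences are not supported.

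- Toxicity will not necessarily be understated. A completer rule also removes event-free patients, and the documents give no non-completion rate. The 13.3% to 2.2% range around 12.0% is illustrative only.
- The primary test is not shown to be inflated. Its false-positive rate stays at or below 9.8% under neutral exclusions. The 16.3% (4 to 6 exclusions) and 25.2% (7 exclusions) figures need every excluded patient to have moderate-to-severe fibrosis, and an exact test.
- No dose or stopping decision rests on this sentence.

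**What to change.** Replace the first sentence of 12.4.1 with a set for each endpoint:

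- **Safety:** all patients given any fresolimumab.
- **PFS, recurrence and local control:** all patients who start study treatment, with time still counted from enrollment for PFS and recurrence as in 10.2, losses to follow-up censored, and local control censored as in 12.4.2. Report enrolled but untreated patients.
- **Fibrosis (evaluable):** all treated patients with a scorable scan in the window, whatever other visits or doses they missed. Define treated in the text, for example at least one fresolimumab dose and SABR.

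In 10.1 and 12.4.1, limit the two exclusion sentences to the fibrosis endpoints. Report the number and cause of exclusions, including any possible study-drug pneumonitis.

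Optionally, repeat the primary test with excluded treated patients counted as moderate-to-severe. This should be supportive only because it is conservative. With 5 neutral exclusions out of 50 and cutoff 33, success needs at most 28 events in the 45 scored. That gives P(X <= 28 | 45, 0.60) = 67.3%, against 77.5% for the primary test at n = 45, and a false-positive rate of P(X <= 28 | 45, 0.75) = 3.9%.

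The cost is some wording and one table of exclusions. No new data are needed, since 4.2.5 and 7.3 already provide for follow-up and adverse event collection in these patients. The sample size and primary test stay as they are. The downside is that some reported figures may be slightly less favourable.

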4.2. Drug Therapy

4.2.1 Fresolimumab Administration

Fresolimumab will be administered IV at a dose of 3 mg/kg on Days 1, 15, and 36, with SABR (-1/+5 days) being administered at 12.5 Gy/fraction in 4 fractions between Days 8 and 12.

Administration Schema:

** -1/+5 days to allow for weekends and holidays and unforeseen circumstances

* +/- 6 days to allow for weekends and holidays and unforeseen circumstances

Phase 1 (see study Schema, pg 9):

We will enroll 5 patients at 3 mg/kg of fresolimumab.

Dose limiting toxicity (DLT) is defined as the following grade 3; 4; or 5 CTCAE v4 events determined to be of possibly; probably; of definite relationship to treatment; occurring after 1st dose of fresolimumab and up to 30 days after the last dose of fresolimumab:

- 1) Radiation pneumonitis, or
- 2) Bronchopulmonary hemorrhage

Of the 5 patients, if none experience DLT, then 3 mg/kg will be the dose for the Phase 2 component.

If one patient experiences DLT, an additional 5 patients will be enrolled at 3 mg/kg. If no more patients experiences DLT, then 3 mg/kg will be the dose for the Phase 2 component. If 2 or more patients experience DLT in the total expanded cohort (or 2 or more patients in the initial cohort experience DLT), then the investigational dose of fresolimumab will be changed to 1 mg/kg. If 2 or more patients in the initial cohort experience DLT before all 5 patients have been enrolled, the remaining patients will receive the lower dose of 1 mg/kg.

At the lower dose (1 mg/kg), 5 more patients will be enrolled. If no more patients experience grade 3 or higher toxicity, then 1 mg/kg will be the dose for the Phase 2 component.

If one or more patients of 5 experience DLT at the reduced dose, the investigators will consider closing the study.

Phase 2:

Fresolimumab will be administered IV at the dose determined from Phase 1 on Days 1, 15 (+ 6 days), and 36 (+/- 6 days), with SABR (-1/+5 days) being administered at 12.5 Gy/fraction in 4 fractions between Days 8 and 12.

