"Presence of moderate-to-severe fibrosis" at 12 months will be defined as severity fibrosis scores 1 or 2 (ie, "Severe" or "Moderate") . This will serve as the primary endpoint for Phase 2.

Pattern and severity of fibrosis at 6 months and pattern of fibrosis at 12 months will be evaluated as secondary endpoints for both Phase 1 and 2 of the study.

Patients who are lost to follow-up and who do not have a scan within +/-6 months of the 12-month time point will be excluded from analysis. Patients who develop inflammatory lung conditions unrelated to radiotherapy (i.e. pneumonia, ARDS, drug-induced pneumonitis, etc.)

will be excluded from the final endpoint analysis if the area of unrelated inflammation impedes scoring of fibrosis severity of the irradiated lesion.

Quantitative image analyses:

Finally, we will explore quantitative image analysis metrics for evaluating radiation fibrosis. This will include analyses such as contouring the region of fibrosis and quantifying its volume relative to the total lung volume and/or the original dose distribution. Similarly, FDG-uptake metrics will be examined on the follow-up PET/CT.

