12.5.2 Sample Size Justification

Phase 1:

Post-SABR pneumonitis grade 3 or greater is expected to occur in $\leq 10\%$ of patients with stage I disease. Based on this percentage, we propose to start out with a cohort of 5 patients at the pre-selected dose of 3 mg/kg of fresolimumab. If one patient develops DLT, then 5 more patients will be enrolled at the same dose to make a total of 10 patients. If no more patients

experience DLT, then the total percentage of patients experiencing DLT is 10% and is considered acceptable for toxicity.

Phase 2:

A sample of size 50 was chosen in order to have 80% power to detect a decrease in the incidence of post-SABR moderate-to-severe fibrosis from 75% to 60% with a one-sided significance level of 10%.

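### The primary analysis excludes patients whose lesion is obscured by drug-induced pneumonitis without exempting fresolimumab, and no analysis puts them back, so the rule can bias the fibrosis rate in a direction the plan cannot show

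*Combined protocol and SAP*

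**What the plan says.** Section 12.4.1 (Analysis Population) gives the rule: "Patients who develop inflammatory lung conditions unrelated to radiotherapy (i.e. pneumonia, ARDS, drug-induced pneumonitis, etc.) will be excluded from the final endpoint analysis". It applies only where the inflammation prevents scoring of fibrosis severity in the irradiated lesion. Section 10.1, which describes the image scoring, repeats it: such patients "will be excluded from the final endpoint analysis if the area of unrelated inflammation" has that effect. The criterion is lack of relation to radiotherapy, not to study treatment, and neither section limits the drug in question to drugs other than fresolimumab.

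Section 12.4.2 makes the scored patients the analysis set. The fibrosis rate "will be tested in evaluable patients in a one-sample one-sided test of proportion comparing the observed rate" with a historical rate of about 75%. Section 10.1 says the historical controls had the same SABR dose without fresolimumab. It assigns scoring to at least two blinded readers by consensus. It does not say who decides that inflammation is unrelated to radiotherapy, and it does not expressly say who decides that scoring is impeded. No sensitivity analysis for the excluded patients is given.

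The Phase 1 toxicity definition in section 4.2.1 uses a wider idea of attribution: "events determined to be of possibly; probably; of definite relationship to treatment". It serves a different purpose and does not govern this exclusion, but it shows that the protocol can refer to treatment as a whole when it means to.

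**The concern.** The exclusion is applied after treatment, for a condition the study drug might cause. If fresolimumab inflames the lung around the lesion, the affected patient can leave the primary endpoint as having an inflammation unrelated to radiotherapy. The historical cohort could not lose anyone for that reason, and the documents do not say whether any of the same exclusions were applied to it. The trial rate and the benchmark may therefore come from differently selected patients.

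The trial is single-arm and open-label, and section 7.12 has the investigators review toxicity and efficacy data every 6 months. An unassigned causal judgement that decides who enters the primary analysis is exposed in that setting. At stake is the one comparison on which the Phase 2 conclusion rests, at a sample size where a handful of patients can change the result.

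**Working it through.** **Inputs.** Section 12.5.2: "A sample of size 50 was chosen in order to have 80% power to detect a decrease in the incidence of" "moderate-to-severe fibrosis from 75% to 60% with a one-sided significance level of 10"%. So n = 50, null rate 0.75, alternative 0.60, one-sided 10%. Section 12.4.2 does not name the form of the test; I assume the exact binomial, since the confidence interval there is exact. The frequency of exclusion is not stated and is an assumption throughout.

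**Step 1: the plan's own figure.** Normal approximation:
n = [(1.2816·√(0.75·0.25) + 0.8416·√(0.60·0.40)) / 0.15]² = 41.6, so 42. With continuity correction: (41.58/4)·[1 + √(1 + 2/(41.58·0.15))]² = 48.02, so 49. Exact test at n = 50: success needs at most 33 events, since P(X ≤ 33 | 50, 0.75) = 0.098 and P(X ≤ 34 | 50, 0.75) = 0.163. Power at 60% is P(X ≤ 33 | 50, 0.60) = 84.4%. The stated 50 is reproduced closely enough. (Section 12.4.2 anticipates a rate "which is expected to be at most 58%, to the historically observed rate of ~75"%; the 58% does not enter the false-positive checks below.)

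**Step 2: direction.** Let a patient who would score moderate-to-severe (an event) be excluded with probability qE, and one who would not with probability qN. The true rate among scored patients is
0.75(1 − qE) / [0.75(1 − qE) + 0.25(1 − qN)].
- qE = 0.10, qN = 0: 0.675/0.925 = 73.0%, which favours the drug.
- qE = qN: 75%, no bias.
- qE = 0, qN = 0.10: 0.75/0.975 = 76.9%, which works against the drug.

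**Step 3: false-positive chance.** Draw X ~ Bin(50, 0.75), remove events and non-events with probabilities qE and qN, and rerun the exact 10% test on those left. Summing over all outcomes, against 9.8% with no exclusions:

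| Who is excluded | 5% | 10% | 15% |
|---|---|---|---|
| Only would-be events (expected 1.9, 3.8, 5.6 patients) | 10.4% | 13.2% | 17.3% |
| Unrelated to the score (2.5, 5.0, 7.5 patients) | 7.6% | 7.6% | 7.5% |
| Only would-be non-events (0.6, 1.3, 1.9 patients) | 6.6% | 4.3% | 2.7% |

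The middle row is below 9.8% because the exact test is discrete at the smaller sample sizes, not because of bias.

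**Step 4: how many exclusions change a result.**
- Start from 34/50 (p = 0.163, fails) and exclude only events: 33/49 p = 0.142; 32/48 p = 0.123; 31/47 p = 0.106; 30/46 p = 0.090. Four exclusions turn failure into success; one to three do not.
- Start from 33/50 (p = 0.098, succeeds) and exclude only non-events: 33/49 p = 0.142. One exclusion turns success into failure; five give 33/45, p = 0.454.

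**Step 5: what restoring patients shows.** Take a result just inside the boundary and count the excluded as moderate-to-severe. With one to three exclusions it becomes 33/50, p = 0.098, and stands. With four, 30/46 becomes 34/50, p = 0.163, and does not. With ten, 25/40 becomes 35/50, p = 0.252.

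**The case against.** A reader might infer that the rule flatters the drug, on the ground that the patients removed are those with the most opacity. The documents do not support this. These patients are excluded because the lesion cannot be scored, so their fibrosis status is unknown, and inflammation over the lesion is not radiation fibrosis. Step 2 shows the bias can run either way. This objection stands in full and limits the conclusion to a bias of unknown direction.

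Fresolimumab pneumonitis at the time of scoring may also be uncommon. The last dose is planned around Day 36 and section 5.2 gives a terminal half-life of 2 to 3 weeks. At three weeks, the 12-month scan falls about (365 − 36)/21 ≈ 16 half-lives later. Section 7.1.2 does not list pneumonitis among the common reactions. Concomitant medication is allowed, so other drugs are possible causes. This bears on frequency, which the documents do not give. Persistent injury, or a scan near the early edge of the ±6-month window, remains possible.

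Because the rule sits in the scoring section, it is reasonable to read it as leaving scorability to the blinded readers. That is fair; attribution of cause is the clearer gap.

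Lung toxicity is still captured by CTCAE scoring, adverse event tables and pulmonary function tests. True, but those do not correct the primary rate, and the toxicity stopping rule in section 7.12 names only radiation pneumonitis and bronchopulmonary hemorrhage.

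Finally, counting drug pneumonitis as fibrosis in the primary analysis would create a composite endpoint set against a fibrosis-only benchmark. That objection is sound, and the fix avoids it.

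**Conclusion.** The concern holds as a defect in the definition of the primary analysis set: a post-treatment exclusion that may depend on the study drug, with no counterpart for fresolimumab in the benchmark cohort, no named assessor of cause, and no analysis to bound its effect. It is not evidence that the reported rate will be too favourable.

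The size depends on two things the documents leave open: how many patients are excluded, and how they would have scored. With exclusion probabilities of 5 to 15% and a true rate of 75%, the false-positive chance lies between 2.7% and 17.3%, against 9.8% without exclusions. The upper figure requires that only would-be events are lost. With very few exclusions, a result reached by losing events is robust: one to three do not rescue 34/50. All figures assume 50 treated Phase 2 patients, an exact one-sided 10% test, and no losses for other reasons. The change is worth making before the analysis, because it is cheap and protects the main conclusion in both directions.

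**What to change.** In sections 10.1, 12.4.1 and 12.4.2:

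1. Before excluding a patient, score another scheduled or clinically obtained scan inside the existing ±6-month window on which the lesion can be read.
2. State that the blinded readers of section 10.1 decide whether inflammation impedes scoring. Say who attributes the cause. Pneumonitis possibly, probably or definitely related to fresolimumab should not be set aside as unrelated unless those patients enter the bounding analyses in item 4.
3. Report the number excluded, with reasons, and say whether the same exclusions were applied to the historical cohort.
4. Repeat the primary rate and test with all excluded patients counted as moderate-to-severe, and again with all counted as none or mild. A positive claim should state whether it survives the first.

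Do not count drug pneumonitis as fibrosis in the primary analysis itself.

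The cost is wording in these sections and one extra tabulation, with no additional study scans or readers. The conclusion may look less favourable if it does not survive the first bound.
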